APPENDIX 5: Adverse Event Reporting

Completing the Adverse Event Case Report Form (CRF)

- Each adverse event must be reported using the Adverse Event (AE) CRF. If necessary, multiple AE CRF forms may be used for participants.
- After completing the header fields, the clinician should write a brief description of the event on the AE CRF and use the standard definitions provided to indicate:
 - (a) the maximum severity of the AE
 - (b) the current status of the AE
 - (c) date of onset of the AE and, if AE has been resolved, date of resolution
 - (d) whether the AE was expected or unexpected the likelihood that the AE is related to the study treatment intervention.

These ratings are described in detail below.

If a participant did not experience an AE at the end of his/her study period (including follow-up), the clinician will indicate this on the AE CRF. In this case, the clinician will not fill out any other fields on the AE CRF except for the header fields, the Source Document Language field, and Form Completion Status field (filled in as 'Form Completed as Required'). There should be at least one AE CRF completed for each participant, even if a participant did not experience an adverse event during the course of the protocol.

AE Severity Rating

The clinician will rate the severity of each AE using a four-category scale. These categories are defined below. This rating should represent the maximum severity of the adverse event. For example, a participant may report multiple headache events over a short period of time or a prolonged period of chest pain that may vary in intensity. The clinician should provide a rating of the most severe episode of headache or a rating of the chest pain at its maximum severity. The numerical rating of the appropriate category should be recorded in the box marked "Severity."

- 1. Mild: Does not interfere with participant's usual function
- 2. Moderate: Interferes to some extent with participant's usual function
- 3. Severe: Interferes significantly with participant's usual function
- 4. Life-Threatening: Poses a significant threat to the life or functioning of the participant

It should be noted that judgments of AE severity should be independent of judgments regarding whether or not an AE is considered "serious." The term "severe" is typically used to describe the intensity (severity) of an event (as in mild, moderate, or severe pain); the event itself may be of regarded as medically benign (such as severe migraine

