headache). This use of "severe" is not the same as "serious," the latter of which is based on participant/event outcome or action criteria usually associated with events that pose a threat to the participant's life or vital functions. Seriousness (not severity) serves as a guide for defining regulatory reporting obligations.

Adverse Event Current Status

The clinician will indicate the current status of the AE at the time of the report using a four-category scale. These categories are described below. The numerical rating of the appropriate category should be recorded in the box marked "Status." In addition, the recorder should indicate the date of the onset of the AE in the boxes provided on the AE CRF.

- 1. New: This report represents the first occurrence of the adverse event
- 2. **Resolved**: The event is no longer ongoing although there still may be lasting problems or complications. If event is resolved, please record the Date and Time of Resolution in the boxes provided on the AE CRF.
- 3. New and Resolved In Same Interval: The AE meets criteria for both New and Resolved AE.
- 4. **Ongoing**: The AE has not been resolved at the time of report.

The Expected or Unexpected Nature of the AE

The clinician will check the appropriate box to indicate whether the AE is expected or unexpected based on the following criteria:

- Unexpected Adverse Event: An adverse event that occurs during the research protocol in which the nature, severity, or frequency of the event is not consistent with either:
 - a. the known or foreseeable risk of adverse events associated with the procedures involved in the research that are described in (a) the protocolrelated documents, such as the IRB-approved research protocol, any applicable investigator brochure, or the current IRB-approved informed consent document, and (b) other relevant sources of information; or
 - b. the expected natural progression of the underlying disease, disorder, or condition of the participants(s) experiencing the adverse event and the participant's predisposing risk factor profile for the adverse event.
- Expected Adverse Event: Any event that does not meet the definition of unexpected adverse event.

Adverse Event Related to Protocol Treatment

The clinician will rate the likelihood that the adverse event was caused by the procedures involved in the research using the following categories and definitions:

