- Reasonable Possibility: There is a reasonable possibility that the adverse event, incident, experience or outcome may have been caused by the procedures involved in the research. A *reasonable possibility* is defined as more likely than not the event is causally and consequentially related to the research procedures or, in other words, there is a strong (>50%) likelihood of the event having been caused by the procedures involved in the research
- Not Reasonable Possibility: There is not a reasonable possibility that the adverse event may have been caused by study participation.

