The PI and Site Investigators continually monitor safety issues at his/her site and report any problem to the Administrative Core at the University at Buffalo. As noted in the Chapter on Trial Governance, the IBSOS will identify a safety officer who functions as an independent evaluator (external to the study) of all adverse events (AEs), both serious and non-serious. In the case of this unmasked trial, the safety officer will work with the investigators to assure that the event is fully documented. Safety officers also review adverse event data to assess if the frequency of the AEs changes dramatically from baseline during treatment delivery phase of the trial. This change could be across the study or a change in the AE profile at a specific site.

Exclusions

Persons with medical or psychological contraindications will be deemed ineligible to be enrolled.

Institutional Review

Prior to study implementation, the protocol, informed consent forms, and all advertising materials must be approved by the IRB of each participating study site. All protocol amendments effecting the safety and welfare of study participants must be approved by the IRB prior to implementation. The study site PI is responsible for all submission documents and for periodic review reports required by the IRB.

Data Security and Confidentiality

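### The adverse event relatedness category is labelled a reasonable possibility but defined as more than 50% likely, so possibly caused events are coded as having no reasonable possibility of causation

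*Protocol*

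**What the plan says.** Appendix 5 of the protocol (Adverse Event Reporting) sets out how relatedness is recorded. Under the heading on events related to protocol treatment, the instruction is: "The clinician will rate the likelihood that the adverse event was caused by the procedures involved in the research using the following categories and definitions". Two categories follow, and no others.

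- **Reasonable Possibility.** Its first sentence reads: "There is a reasonable possibility that the adverse event, incident, experience or outcome may have been caused by the procedures involved in the research". The next sentence says that a reasonable possibility "is defined as more likely than not the event is causally and consequentially related to the research procedures", and restates this as meaning that "there is a strong (>50%) likelihood of the event having been caused by the procedures involved in the research".
- The other is **Not Reasonable Possibility**. It has no threshold of its own and reads: "There is not a reasonable possibility that the adverse event may have been caused by study participation".

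The rating is one of the items that the clinician must complete on the adverse event form. The form instructions at the start of Appendix 5 describe that item as "the likelihood that the AE is related to the study treatment intervention".

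Appendix 9 (Human Subjects Protection) adds a safety officer who "functions as an independent evaluator (external to the study) of all adverse events (AEs), both serious and non-serious". Section 3.4 lists safety among the secondary endpoints, measured by whether adverse events occur.

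**The concern.** The label and first sentence describe a low bar: the event may have been caused by the research. The definition sets a much higher one: the event was probably caused by it. With only two categories, everything between clearly unrelated and probably related has to go somewhere, and the definition sends it to the category that denies any reasonable possibility.

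Two things are at stake. First, a table of related events built on this rating would mislead its reader, because the column heading would say reasonable possibility while the contents were probable causation. Second, the text supports two ways of coding the same event. A rater who works from the label and a rater who works from the number can disagree, and both can point to the protocol. The trial has two clinical sites, so such a difference could run along site lines.

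Intermediate judgements are foreseeable here. Appendix 6 gives clinical deterioration and significant suicidal ideation during active treatment as examples of reasons for withdrawal. Appendix 5 itself recognises natural progression of the underlying condition as an explanation for an event, so competing causes will often be in play.

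This is a definition fixed in the protocol for a form that is filled in once. An analysis plan cannot restore a distinction that was never recorded.

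**Working it through.** No sample size, power or error rate is involved, so there is nothing to recompute. The check is to apply the rule as written and compare it with the wording of its own label.

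**Inputs**, all from Appendix 5: the rating scale (judged likelihood of causation, here called p), the label and first sentence of category 1, the definition of category 1, and category 2.

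**Step 1: the rule under the definition.** If p > 50%, the event is Reasonable Possibility. Category 2 is the negation of category 1, so p ≤ 50% is Not Reasonable Possibility. There is no third option.

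**Step 2: the rule under the label and first sentence alone.** The event is Reasonable Possibility whenever the rater thinks that there is a reasonable possibility that it may have been caused by the procedures. No number is attached.

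**Step 3: compare for example values of p.**

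| Judged likelihood p | By the definition | By the label and first sentence |
|---|---|---|
| 60% | Reasonable Possibility | Reasonable Possibility |
| 50% | Not Reasonable Possibility | Reasonable Possibility |
| 40% | Not Reasonable Possibility | Reasonable Possibility |
| 30% | Not Reasonable Possibility | Reasonable Possibility on an ordinary reading |
| 20% | Not Reasonable Possibility | Open to the rater, but plausibly Reasonable Possibility |

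The two readings agree above 50%, and also at the bottom of the scale, where nobody would call causation reasonably possible. They part over the band between, whose upper end is 50% and whose lower end the protocol does not fix.

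**Step 4: wording inside the definition.** More likely than not and strong are offered as equivalents, tied to the same figure of more than 50%. A likelihood just above one half is more likely than not, but few raters would call it strong. This is a further, smaller source of inconsistent coding.

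**Step 5: what is being rated.** The object changes within the appendix. The form instructions refer to the study treatment intervention, the category 1 text to procedures involved in the research, and the category 2 text to study participation. These are not the same. An event brought on by an assessment interview, for example, arises from a research procedure and from participation, but not from the treatment. As worded, the two categories are not strict complements even apart from the threshold.

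**The case against.** The strongest reply is that the protocol makes reasonable possibility a defined term. A definition narrower than everyday usage is a poor choice of label, but a rater who reads to the end of the bullet has one rule. On this view, events at or below 50% fall by complement into the second category. That stands: a reader might infer that such events fit neither category, and the text does not support this. They have a place, but it is one whose wording misdescribes them. The reply does not remove the mismatch between label and content, nor the risk that raters use the label.

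The second reply is that nothing in the protocol turns on the rating, and on the text shown this is also right:

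- The safety endpoint in Section 3.4 is the occurrence of adverse events, with no relatedness filter.
- Appendix 5 requires every adverse event to be entered on the form, and makes seriousness the guide to regulatory reporting.
- The safety officer in Appendix 9 evaluates all events and looks for changes in their frequency.
- Prompt reporting of discontinuations to the ethics board (Appendix 9) depends on unanticipated problems with serious risk, and this rating is not named as the trigger.
- No table of related events by arm is promised.

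A reader might therefore infer too much: that the safety endpoint is biased downwards, or that a real signal could vanish. The documents do not support either, since an excess of events would still appear in the overall counts.

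A reader might also try to size the effect by assuming judged likelihoods spread evenly from 0 to 1, which would put half of all events at or below 50%. The protocol gives no such distribution, and that half would include events with near-zero likelihood that any scheme would call unrelated. Nor does the protocol say how often distress during therapy would be judged more than 50% attributable to it.

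**Conclusion.** The point holds as a defect in the relatedness classification, and only there. Followed as written, the rule records every event judged possibly but not probably caused as having no reasonable possibility of causation. Any related-event count drawn from it would mean probably related. Measured against the category's own label, that count would be too low if raters apply the number, and inconsistent if some apply the label.

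The size cannot be stated, because the protocol gives no information on how judged likelihoods will be distributed or on which reading raters will adopt. The conclusion rests on the protocol's own wording and on no outside standard for causality assessment. It assumes that the form uses the two categories as printed.

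The correction is worth making although no endpoint depends on the rating. The rating is a required safety item, the lost distinction cannot be recovered afterwards, and the change is cheap.

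**What to change.** Delete the sentence that defines a reasonable possibility as more likely than not, together with its more-than-50% restatement, so that the category means what its label and first sentence say. The second category then becomes a true negation of the first.

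In the same edit, choose one object of rating (treatment, research procedures or participation) and use it in the form instructions, the section heading, and both categories.

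The cost is a change of wording in Appendix 5 and in the form guidance, with a short note to raters. If any events have already been rated, their forms would need to be re-rated or marked as coded under the old definition. The downside is that somewhat more events will be classed as related. Adding a middle category is another option, but it is a choice of scale and is not needed to remove the mismatch.

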APPENDIX 6: Interruption or Discontinuation of Therapy

Definitions of "Withdraw Consent" & "Lost to Follow-Up"

A participant can partially or totally withdraw consent. If s/he totally withdraws consent, then IBSOS Study personnel may not attempt to collect any further data. But a participant may withdraw consent only for collection of specific data items; for example, quality of life, health care utilization, etc.

Likewise, a participant can be partially or totally lost to follow-up. A participant is partially lost to follow-up if s/he is unable to attend further follow-ups at the clinic but is still willing to provide questionnaire data administered via mail. This can happen if the participant moves away from the clinical center's city, or has a condition (e.g. unstable heart disease) that conflicts with the aims of the trial that was not disclosed during pre-treatment evaluation.

A participant is totally lost to follow-up if s/he dies or his/her whereabouts are unknown, that is, s/he has disappeared according to all available contacts. In this case, generally no further data can be collected.

Withdrawal from the Study

Following enrollment, participants may discontinue or be discontinued from study participation for the following reasons:

- 1. Voluntary withdrawal of consent by participant/volunteer/participant.
- 2. Withdrawal requested by the study site's Principal Investigator S/he may remove a participant from the trial if, in his or her opinion, it is not in the best medical interest for the volunteer to continue in the IBSOS trial.

Examples include situations where participants experience significant clinical deterioration (e.g. significant cognitive or medical deterioration, suicidal attempts or significant suicidal ideation, or significant substance use) during the 'active' (i.e. acute) phase of treatment that may require treatment that is outside the scope of study protocol (e.g. hospitalization). In such cases, participants are withdrawn from the treatment arm of the study and encouraged to seek appropriate treatment at a qualified facility.

3. **Protocol violation and noncompliance with trial procedures** — The investigator may believe that the volunteer is not complying with the protocol or has violated protocol criteria and may therefore wish to withdraw him/her from the trial.

Examples of noncompliance arise if a participant fails to attend two consecutive MC-CBT or S-CBT sessions, or three consecutive EDU sessions without a reason deemed appropriate by his or her therapist and site PI. Non-compliance with homework is not regarded as an acceptable basis for withdrawal.

4. **Administrative error** — Participants who do not meet all study inclusion or exclusion criteria may enter the study in error.

For example, a participant who does not disclose concurrent targeted psychotherapy for IBS or the presence of a medical condition that makes it unsafe or impractical for the participant to continue may be withdrawn at the PI's discretion. These participants may be replaced because they would not have satisfied eligibility criteria had the participant fully disclosed information regarding health status at the time eligibility was determined.

			Page 1 of 2
DATA COLLECTI	ON FORMS S	CHEDULE	00-00-00
ST	UDY IBSOS1 BOOK 1		
NOTE: The columns are marked with an "X" to indicate data and evaluation	ns required at each visit.	PRE-TREATMENT BASELINE	PREMATURE DISCONTINUATION
eData/HAND-ENTERED FORMS	Frontier Form #/ Reference		
IBS0S1 Study Participant Intake Form	QLW01	×	
IBS - Symptom Severity Scale	QLW03	×	
TEV- BL	QLW10	×	
IBSOS Comorbid Disease Form	QLW13	×	
MD Rating - Baseline	QLW15	×	
Concomitant Medications/Supplements and Non-Drug Therapies	CMW1	×	
IBS Module (IBS-PRO)	QLW14	×	
IBSOS1 Study Participant Economic Form	QLW06	×	
FMBS	QLW12	×	
Euroqol EQ- 5D	QLW02	×	
Adverse Events	IBS0021		×
Off Study / Drop Out	IBS1601		×
Missed Visit	ST0010		
Death Form	SP1411		
FLIPS FORMS	Frontier Form #/ Reference		
IBS - LOC	ibsloc	×	
IBS SE Questionnaire	ibsse	×	
bSS	bss	×	
PCSQ-2 Item	pcsq2	×	
IBS-QOL Instrument	ibsqol	X	
McGill - SF	mcgsf	×	
The SF - 12 Health Survey	sf12	×	
Restorative Activities	restact	×	
SOMS-7	soms7	×	
ASI	asi	×	
NSI	vsi	X	
Continued on page 2.			

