5. ASSIGNMENT TO TREATMENT GROUPS

5.1 Randomization

Participants in the IBSOS will be randomly assigned to one of three treatments. Random assignment is important to ensure that the different experimental treatments will be given to comparable groups of participants. Treatment assignments will be generated using an existing web-based participant registration and randomization system at Frontier Science. This system uses protocol-specific specifications files to present questions to the sites to evaluate a participant for eligibility. Only participants who meet all the eligibility requirements can be randomized to the study. The participant enrollment system also collects basic demographic information at the time of enrollment. The Protocol Data Manager at Frontier Science will work with the Principal Investigator and Project Statisticians to develop these files based on the eligibility criteria of the protocol. Treatment allocation assignments are stratified by clinic site. This will ensure initial comparability between groups of eligible participants, for whom treatments are compared, thus eliminating the impact of individual and site difference variables on outcome.

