The IBSOS is designed to assess both the immediate and long-term follow-up benefits of CBT for IBS, as well as its clinical course. To achieve these objectives, it is essential that each participant be examined regularly at follow-up visits until the study is terminated. Follow-up assessments are scheduled two weeks after treatment ends and every three months thereafter (three, six, nine, and 12 months).

Study Visit Windows

Follow-up assessments will be conducted in person, at appointments scheduled by the PC specifically for this purpose. Scheduling should occur by telephone when possible; participants who do not have telephones will be contacted by mail and asked to make arrangements for an appointment. Participants may also make appointments in person. A minimum of three contact attempts should be made and documented before a patient is considered unreachable. If a patient cannot be contacted, inform the SI after two attempts have been made, and before ruling a patient unreachable. Every conceivable effort must be made before a participant is deemed unreachable. Participants who are lost to follow-up during the active treatment phase, however, are allowed and should be encouraged to participate in regularly scheduled follow-up assessments. *All participants, regardless of whether or not they completed therapy, should be contacted for all follow-up assessments and compensated for their time.*

We ask that every effort be made to adhere to the specific time windows when performing the follow-up assessments. If this is not possible, the window can be extended for purposes of recording the visit. However, **extensions should be** *regarded as the exception and not the rule.*

- Two-week post-treatment Post-treatment assessment should occur two weeks following the end of active therapy. However, it is permitted for post-treatment follow-up visits to occur within the two weeks preceding or following the scheduled appointment (i.e. weeks 10-14).

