APPENDIX 9: Human Subjects Protection

Informed Consent

Because the study will rely on intent to treat (ITT) (vs. completer) approach for data interpretation, all randomized participants will be included in study analyses. Therefore, it is important to have information on as many participants as possible. If a participant is unwilling to continue full engagement in the study, every effort should be made to strongly encourage the participant to undergo regularly scheduled follow-up clinic evaluations, and, if this is impossible, a minimum-level contact (telephone interview).

Documenting Withdrawal of Consent

If a participant indicates that s/he wishes to withdraw consent, his/her wish must be honored. Just as it is a severe ethical breach to enroll a participant without her consent, so it is a severe ethical breach not to honor her withdrawal of consent. At all times during this process, the participant should be treated with the utmost respect and courtesy. This is his/her due, of course, but also, participants sometimes change their minds and may return to the study if they are shown respect and courtesy.

Procedures for Discontinuation

A participant's decision to withdraw from a clinical trial should be documented in the study records using the Off Study (i.e. drop out) Form. At a minimum, such documentation should include:

- Whether the discontinuation of the participant's participation resulted from a decision by the participant or by the investigator;
- Whether the discontinuation involves some (e.g. treatment but not follow up assessments) or all types of participation;
- The reason for the discontinuation.

An individual report should be promptly submitted to the site IRB if the discontinuation was related to an unanticipated problem involving serious risks to the participant. Otherwise, premature discontinuations can be summarized in regularly scheduled reports for DSMB.

Follow-Up

Once participants have signed on to the study, we become responsible for following them up to five times over the following 12 months — regardless of whether they enter or complete treatment. The first challenge is simply maintaining contact; the second is getting them to come in and complete the assessments.

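### Appendix 6 permits withdrawal from the trial for non-attendance, at limits that differ by arm, and replacement of late-found ineligibles, against the follow-up and analysis of everyone in Appendices 8 and 9

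*Protocol*

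**What the plan says.** The Protocol's Appendix 6, under Withdrawal from the Study, opens its list by saying that "participants may discontinue or be discontinued from study participation for the following reasons". Two of the four reasons matter here.

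- **Reason 3, non-compliance.** The investigator "may therefore wish to withdraw him/her from the trial". The example is a participant who "fails to attend two consecutive MC-CBT or S-CBT sessions, or three consecutive EDU sessions", provided the absence is "without a reason deemed appropriate by his or her therapist and site PI".
- **Reason 4, administrative error.** A participant who entered in error may be withdrawn at the PI's discretion, and "These participants may be replaced because they would not have satisfied eligibility criteria".

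Two other appendices point the other way. Appendix 8, Study Visit Windows: "All participants, regardless of whether or not they completed therapy, should be contacted for all follow-up assessments". Appendix 9, Informed Consent: "all randomized participants will be included in study analyses".

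On format, Section 2.1 gives S-CBT ten weekly sessions and the other two arms four clinic visits over ten weeks. Section 6.3 says the control format parallels MC-CBT, including two short phone calls.

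**The concern.** A site that follows Appendix 6 literally can end study participation for people whom Appendices 8 and 9 require it to keep following. An ITT label cannot recover outcomes that were never collected.

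The exposure is not the same in each arm. The non-attendance example is stricter for both CBT arms than for the control, and S-CBT applies it over more sessions. The judgement on whether an absence is excused lies with the therapist, who knows the arm, and the site PI, in a trial that Appendix 9 calls unmasked. Poor attenders are unlikely to resemble the rest of their arm. Loss of outcomes among them that differs by arm could bias both the CBT-versus-control comparisons and the S-CBT versus MC-CBT equivalence comparison, in either direction.

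The replacement sentence adds a second opening. It does not say whether the person replaced stays in the analysis.

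**Working it through.** **Passages side by side**

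| Question | Appendix 6, reasons 3 and 4 | Appendices 8 and 9 |
|---|---|---|
| What ends? | Study participation | Treatment may end; follow-up goes on |
| Who is analysed? | Not stated; replacement allowed | All randomized |
| Is the attendance limit the same in each arm? | No: 2, 2 and 3 consecutive misses | Not addressed |

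EDU is read as the attention control, since Section 6 describes that arm as education and supportive counselling. That reason 4 concerns randomized people is an inference from Section 5.1: "Only participants who meet all the eligibility requirements can be randomized to the study". An eligibility error found later would then normally concern someone already randomized.

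**Exposure to the limit.** The Protocol states no attendance, dropout or withdrawal rate by arm, so there is no planned figure to reproduce. The per-session miss rate *p* is an assumption. Inputs from the Protocol: S-CBT 10 sessions, limit 2; MC-CBT 4 sessions, limit 2; control 4 sessions, limit 3; 160 per arm.

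*Model A: each session is missed without an accepted reason, independently, with probability p.*

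- Limit 2, any number of sessions: let Q(j) be the chance of no two consecutive misses in j sessions. Then Q(j) = (1−p)·Q(j−1) + p(1−p)·Q(j−2), with Q(0) = Q(1) = 1. The chance of meeting the limit is 1 − Q(n).
- For n = 4 this equals 3p² − 2p³. At p = 0.10: 0.030 − 0.002 = 0.028.
- Limit 3 in 4 sessions: 2p³ − p⁴. At p = 0.10: 0.0020 − 0.0001 = 0.0019.
- For n = 10 and p = 0.10: Q(10) = 0.9197, so 0.0803.

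| p | S-CBT | MC-CBT | Control | S-CBT / control | MC-CBT / control |
|---|---|---|---|---|---|
| 5% | 2.1% | 0.7% | 0.02% | 88 | 30 |
| 10% | 8.0% | 2.8% | 0.2% | 42 | 15 |
| 15% | 16.7% | 6.1% | 0.6% | 27 | 9.7 |
| 20% | 27.3% | 10.4% | 1.4% | 19 | 7.2 |
| 30% | 50.4% | 21.6% | 4.6% | 11 | 4.7 |

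Per 160 participants, p = 10% gives 12.8, 4.5 and 0.3; p = 20% gives 43.7, 16.6 and 2.3. If the two phone calls count as sessions (six contacts in the control arm), the S-CBT to control ratio over the same range of p runs from 44 down to 6.

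*Model B: permanent stopping, with the first missed week uniform over weeks 1–10 and the four visits at weeks 1, 5, 8 and 10.*

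- S-CBT: at least two sessions remain if stopping is by week 9, so 9/10 of stoppers meet the limit.
- MC-CBT: at least two visits remain if stopping is by week 8, so 8/10.
- Control: at least three visits remain if stopping is by week 5, so 5/10.
- Ratios to control: 0.9/0.5 = 1.8 for S-CBT and 0.8/0.5 = 1.6 for MC-CBT.

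**How much is due to session count?** If the two-miss limit is applied to every arm under Model A, purely as an illustration, S-CBT still meets it 2.3 to 2.9 times as often as a four-session arm. The like-for-like contrast for the arm-specific limit is therefore MC-CBT against control.

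**Precision.** For the IBS-SS, the Protocol gives a half-width of about 18 (SD 78, 160 per group, with a tolerance allowance). The plain formula gives 1.96 × 78 × √(2/160) = 17.1. If everyone meeting the limit at p = 15% were lost (27 S-CBT and 10 MC-CBT, leaving 133 and 150), it becomes 1.96 × 78 × √(1/133 + 1/150) = 18.2, against a threshold of 50. Precision is hardly touched; the issue is bias.

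**The case against.** The strongest reply is that the Protocol already intends follow-up to continue.

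- Appendix 8 says so directly, and Appendix 9 has the discontinuation record distinguish stopping treatment from stopping everything.
- Appendix 7 lists a form for premature discontinuation of study treatment separate from the off-study form. Its premature-discontinuation column collects outcomes, including the global impression of change.
- Appendix 6 is titled as being about therapy, ends its reason 2 by limiting withdrawal to the treatment arm, and bars further data collection only on total withdrawal of consent.

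This shows the intent. It does not qualify reasons 3 and 4, which name the trial and study participation without that limit. One assessment at discontinuation also does not replace the scheduled week 12 and quarterly outcomes.

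Two stronger readings are tempting and should be resisted.

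1. A reader might infer that the rule removes S-CBT participants far more often than controls, for example about 27 against 1 per 160 at a 15% miss rate. The documents do not support that. Withdrawal is discretionary, the limits are examples, accepted absences are exempt, and no attendance rate is given. The figures are chances of becoming eligible for withdrawal under one assumed pattern.
2. A reader might infer that replacement drops the replaced person from the ITT set. Appendix 6 does not say so, and recruiting an additional participant does not in itself breach ITT. The list also applies from enrollment, a term Section 2 uses for consent before randomization, so replacement after randomization is a plausible reading and not a stated one.

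**Conclusion.** The contradiction stands on the text alone. Appendix 6 permits discretionary withdrawal from the trial under reasons 3 and 4, while Appendices 8 and 9 require follow-up and analysis of everyone. The non-attendance limit differs by arm with no stated reason, most plainly between MC-CBT and control, which share a format.

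The direction was the same in every scenario tried: S-CBT most exposed, then MC-CBT, then control. The size is not known. The S-CBT to control ratio runs from about 1.8 under permanent stopping to about 88 under independent misses at 5%, and all of it rests on assumed attendance. The number of outcomes that would actually be lost cannot be derived from the Protocol, and neither can the size or direction of any bias. No view is taken on which attendance limit is right.

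**What to change.** Align Appendix 6 with Appendices 8 and 9:

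- State that participants withdrawn under reasons 3 or 4 stay in scheduled outcome follow-up unless they totally withdraw consent, die or are totally lost to follow-up, and that they stay in the ITT set in their assigned arm.
- State that replacing a randomized participant is an addition and does not remove the person replaced from the analysis, or delete the replacement sentence.
- Ask the clinical team to reconcile the differing attendance limits or state the reason for them. No limit is proposed here.

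The cost is wording in one appendix, plus follow-up contacts that Appendices 8 and 9 already require.
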